# 4.3.1 Data Collection for withdrawal patient

In case of premature discontinuation from the study for any reason (except in case of withdrawal of consent), the investigator must make every effort to perform the end of study assessments. These data should be recorded in the medical record and eCRF, as they consist of an essential evaluation that should be done prior to withdrawing any patient from the study.

The primary reason for withdrawal will be clearly documented in the patient's medical record and recorded in the eCRF.

If a patient has a premature treatment discontinuation, the treating physician will contact the patient every 3 months for 3 years as part of the post-study follow-up. Patients will be followed until they die or withdraw consent for contact in which case the date of death will be determined from public records (e.g. the Social Security database or publications).

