### 3.4 DURATION OF STUDY

The recruitment of up to 45 patients is expected to approximately cover an 18-month period.

Patients in part 1 may be treated up to 56 weeks: 4 cycles of 2 weeks each followed by 12 cycles of 4 weeks each.

Patients in part 2 may be treated up to 52 weeks: 4 cycles of 2 weeks each followed by 11 cycles of 4 weeks each.

Treatment by ibrutinib will be at least administered until the end of the study follow-up unless a disease progression (IWCLL), untoward toxicity or consent withdrawal leads to the premature interruption of the treatment.

Patients will be followed for 12 months after interruption of IPH2201 treatment (End of Study visit). Furthermore, patients will be enrolled in a post study follow-up enabling the documentation of disease progression (IWCLL) or death for 3 additional years after the completion of their study follow-up.

CONFIDENTIAL

Release date: Edition number

GED version

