# 7.2.4 Overall survival (OS)

OS is defined as the time from study entry until death from any cause, and is measured in the intent-to-treat population.

[figure not shown]

CONFIDENTIAL

Release date: Edition number 12 August 2016

GED version

MOD-3783

[figure not shown]

Release date: Edition number

GED version

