8.4 Remission with undetectable MRD

Undetectable MRD is defined as the percentage of CLL cells of all lymphocytes below 0.01%. The rate of patients in cCR at W52 with undetectable MRD in peripheral blood and bone marrow will be summarized overall and by dose level, and the 95% confidence interval for this rate will be calculated only overall for the patients in the phase Ib and for the patients in the phase IIa. Remission with undetectable MRD needs to be confirmed, i.e. CR and undetectable MRD should be met jointly and confirmed jointly. The rate of remission with undetectable MRD in peripheral blood and in bone marrow will be displayed separately.

8.5 Duration of Remission (DOR), Duration of Complete Remission (DOCR), Progression free Survival (PFS) and Overall Survival (OS)

The duration of Remission (DOR) and duration of complete Remission (DOCR) will be assessed in the main endpoint population, whereas the Progression Free Survival (PFS) and Overall Survival (OS) will be assessed in the ITT/safety population.

The DOR, for the remission assessed at 52 weeks, is defined as the time from the date of first evaluation of the remission (CR or PR) to the first documentation of progressive disease, relapsed disease or death. In case an assessment of a progressive disease, relapsed disease or death record does not exist, the duration of remission is censored at the time of the last disease assessment date. The duration of remission is only calculated for the patients with a cCR, an uCR or a PR assessed at 52 weeks.

The DOCR is calculated similarly for the patients with a cCR assessed at 52 weeks.

The PFS is defined as the time from first dose administration until the occurrence of progressive disease, relapsed disease or death from any cause. Patients without an event at the time of the analysis will be censored at his or her last disease assessment date; patient with no post-baseline assessments will be censored at the day of first dose administration.

The OS is defined as the time from first dose administration until death from any cause. Alive Patients are censored at the most recent date they are known to be alive. Subjects with no assessment post-baseline will be censored at the day of first dose administration.

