The Kaplan-Meier method will be used to display graphically the DOR, PFS and OS for all patients. The number of patients and the number of DOR, PFS and OS events will also be displayed on the graph. The median (with its 95% confidence interval) DOR and DCOR will be displayed. Listing with individual values will also be displayed.

Page 19 of 26

TPL N°: eTPL SA-02-01

TPL Version: 02

Of SOP SA-02.08 TPL Effective Date: 31 Mar 2016

[figure not shown]

9. Safety Evaluation

All safety analyses will be done for the ITT/safety population.

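### After withdrawal of consent for contact, deaths found in public records count towards OS, but survivors are censored at last contact unless another source gives an alive date, so censoring depends on outcome

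*Protocol*

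**What the plan says.** Protocol 4.3.1 deals with patients who stop treatment prematurely. For them, "the treating physician will contact the patient every 3 months for 3 years as part of the post-study follow-up". It then adds: "Patients will be followed until they die or withdraw consent for contact in which case the date of death will be determined from public records". The examples it gives are a social security database and publications. It names no alive date from those sources.

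SAP 8.5 states "The OS is defined as the time from first dose administration until death from any cause", with no limit tied to consent. On censoring it states: "Alive Patients are censored at the most recent date they are known to be alive". It has no rule for withdrawal of consent for contact, for the date on which records are searched, or for a search that finds nothing.

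Two other places bear on survival follow-up. Protocol 4.3 has the sponsor collect survival periodically through the investigator after the End of Study visit. Protocol 9.1.1.5 asks sites to keep following all subjects for survival until the trial ends. Neither says what happens once consent for contact is withdrawn.

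OS is a secondary endpoint in both phases. The planned output is descriptive: "The Kaplan-Meier method will be used to display graphically the DOR, PFS and OS for all patients".

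**The concern.** Take two patients who withdraw consent for contact on the same day. One later dies and is found in the records. That patient stays in the risk set until death and counts as an event. The other survives. On the ordinary reading that patient was last known alive at last contact, and leaves the risk set then. Who is followed after withdrawal is therefore decided by the outcome.

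Kaplan-Meier needs censoring that does not depend on later survival. Here that fails even if the decision to withdraw has nothing to do with prognosis. Deaths are divided by a risk set that has lost the surviving withdrawals, so estimated OS is too low. The trial has no concurrent control arm to share the error. Follow-up is long: after the in-study year it continues "for 3 additional years after the completion of their study follow-up". The error grows with follow-up, and a confidence interval does not reflect it.

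**Working it through.** **1. The plan's own figure.** The documents' only design calculation is for CR (SAP 3.3.2): 27 patients, positive with at least 4 CRs, p = 0.05 against 0.20. The exact binomial upper tail is P(X ≥ 4) = 1 − Σ C(27,k) p^k (1−p)^(27−k), summed over k = 0 to 3. It gives alpha 0.0437 and power 0.8177. The figure reproduces and does not involve OS. No figure is stated for OS or for withdrawal.

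**2. Inputs for scale.**
- Survival: 83% OS at 26 months with single-agent ibrutinib (protocol 1.1.5.1). The exponential form is an assumption: hazard = −ln(0.83)/26 = 0.00717 per month.
- True OS: 0.83^(60/26) = 65.1% at 60 months and 0.83^(24/26) = 84.2% at 24 months.
- Horizon: about 12 months of treatment + 12 in-study + 36 post-study = about 60 months (protocol 3.4). The 24-month result shows a shorter cut-off.
- Withdrawal share (5%, 10%, 20%), its timing, and the fraction of later deaths found in records (50% to 100%) are assumptions, because the documents give none of them.

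**3. Hand check of the mechanism.** Suppose 20 of 100 patients withdraw on day 0, all later deaths are found, and withdrawal is unrelated to prognosis. By 60 months 34.95 of the 100 have died (100 − 65.05), including 20 × 0.3495 = 6.99 of those who withdrew. The 13.01 surviving withdrawals leave at once, so the risk set is 80 + 6.99 = 86.99. Estimated OS = 1 − 34.95/86.99 = 59.8%, or −5.2 points. This is the extreme for 20%; later withdrawal gives less.

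**4. Large-sample Kaplan-Meier under the rule as written.** Withdrawal is non-informative. Estimated 60-month OS (true 65.1%), in %:

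| Withdrawal | Spread over 60 months, 50% capture | Spread over 60 months, full capture | Months 1–18, 50% capture | Months 1–18, full capture |
|---|---|---|---|---|
| 5% | 64.8 | 64.5 | 64.5 | 64.0 |
| 10% | 64.4 | 63.7 | 64.0 | 63.0 |
| 20% | 63.6 | 62.2 | 62.6 | 60.4 |

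The spread columns use a constant withdrawal rate; uniform timing over months 1–60 changes them by at most about 0.2 points. The bias is thus about −0.3 to −1, −0.6 to −2 and −1.5 to −4.7 points for the three rows.

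With a 24-month cut-off and a constant withdrawal rate, the bias is −0.2 to −0.4 (5%), −0.4 to −0.8 (10%) and −0.8 to −1.6 (20%).

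**5. Informative withdrawal.** Let the hazard rise 2- or 3-fold after withdrawal, with 20% withdrawing and a 60-month horizon. Against the true OS of that population (62.4% or 60.8%), the bias is +0.1 or +1.1 at 50% capture, −1.8 or −1.3 at 90%, and −2.2 or −1.8 at 100%. The direction is not fixed.

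**6. Sampling error for comparison.** At N = 27, √(0.6505 × 0.3495/27) = 9.2 points at 60 months and √(0.842 × 0.158/27) = 7.0 points at 24 months.

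**7. The two repairs**, at 20% constant-rate, non-informative withdrawal and 60 months:
- Censor at last contact and ignore later record deaths: 65.0%.
- Search at one date and censor those not found dead there: 66.7%, 65.3% and 65.0% for 50%, 90% and 100% capture.

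**The case against.** A reader might infer that withdrawn patients add deaths but no survival time. The documents do not support that. Those who die contribute all their time to death, and the others contribute time to last contact. Only event-free time after last contact is lost.

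A reader might also infer that OS is certainly understated. That needs three things the documents do not settle:
- **Alive dates.** Protocol 4.3 and 9.1.1.5 may yield alive dates for some of these patients. The SAP also does not say that a search with no match leaves a patient not known to be alive. If the search date served as the alive date, the asymmetry would go.
- **Withdrawal.** It must be unrelated to prognosis, or record capture must be good; step 5 shows the bias can vanish or reverse.
- **Population.** The sentence covers withdrawal of consent for contact after early treatment discontinuation. It does not cover every patient who stops treatment or leaves the study, so 20% may be high for this subset.

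The larger figures combine early withdrawal, full capture and a 60-month horizon. Every figure in the step 4 table is below the sampling error at N = 27. The SAP plans an OS curve with event counts and listings, with no OS landmark rate, median or test, and the CR rule is untouched.

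All of this stands and limits the point. It does not remove it. Neither section says it applies after consent for contact is withdrawn, and the SAP leaves two programmers free to treat a search with no match differently. Sampling error does not excuse a systematic error that one sentence can avoid.

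**Conclusion.** The point holds in a limited form. Followed as written, and unless protocol 4.3 or 9.1.1.5 supplies alive dates, the OS rule makes censoring depend on outcome for patients who withdraw consent for contact after stopping treatment early. With non-informative withdrawal and at least some later deaths found, Kaplan-Meier OS is pulled down.

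At 60 months the size is under about 1 point at 5% withdrawal and at most about 2 points at 10%. At 20% it lies between about 1.5 and 4.7 points. It is nil if nobody withdraws, and less at 24 months. These sizes rest on the exponential hazard and on assumed withdrawal share, timing and capture. The net direction is not guaranteed. The effect is confined to a descriptive secondary endpoint. It deserves correction because the rule itself creates the bias and the correction is cheap.

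**What to change.** In SAP 8.5, give patients who withdraw consent for contact one end of observation that does not depend on outcome. Choose one rule as primary and report the other as a sensitivity analysis:

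1. Search public records for all of them at one recorded date before database lock. Count deaths up to that date, less a stated reporting lag, and censor those with no death record there.
2. Censor all of them at last contact and do not count deaths found later in records.

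The same text should say whether survival information obtained under protocol 4.3 or 9.1.1.5 may be used as an alive date for these patients.

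The cost is a sentence or two in the SAP, one recorded search date and one extra run. Each rule has a weakness. The first overstates OS when capture is incomplete: 66.6% to 67.9% against 65.1% at 20% withdrawal and 50% capture, depending on timing. A reporting lag does not recover deaths that records never show. The second assumes non-informative withdrawal: if the hazard doubles after withdrawal, it gives 64.8% against a true 62.4% at 20% withdrawal. Reporting both shows how much the choice matters.

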# 4.3.2 Patient Replacement Policy

In any case, if patients do not receive at least 1 administration of IPH2201.

In the two phases of the trial (Ib and IIa), in case of treatment discontinuation of IPH2201 due to disease progression before the end of 8 weeks of treatment.

Release date: Edition number

GED version

# 5 STUDY TREATMENT(S)

# 5.1 Investigational Medicinal Product (IMP): IPH2201

# 5.1.1 Packaging and labelling of trial product

IPH2201 is provided by Innate Pharma in boxes of 4 vials.

This study is open labelled.

Labelling is in accordance with local law and trial requirements. Besides, each vial is identified by a specific and single Dispensing Unique Number (DUN) number.

# 5.1.2 Doses of Investigational Medicinal Product

IPH2201 will be administered by intravenous route, over 1 hour infusion at 1, 2, 4 or 10 mg/kg.

# 5.1.3 Drug preparation and administration instructions

The Investigational Medicinal Product preparation is performed as follow:

DETAILED DRUG INSTRUCTIONS REGARDING RECONSTITUTION AND ADMINISTRATION ARE GIVEN IN THE CURRENT VERSION OF THE TMM.

The TMM is a guideline on how to handle all trial materials supplied by INNATE PHARMA for the trial. It is prepared in order to ensure correct ordering, handling, distribution and storage of the trial materials. All staff involved in the handling of trial materials must follow this guideline.

# 5.1.4 Storage

The storage and shipping conditions for IPH2201 are +5°C +/-3°C.

#### CONFIDENTIAL

Release date: Edition number

MOD-3783

12 August 2016

GFD version

The investigator and/or the pharmacist must ensure the availability of proper storage conditions, including proper temperature monitoring. Calibration of the temperature monitoring unit must be done at least once a year. Preferably, the temperature must be recorded by continuous, automatic, stationary equipment. If the equipment does not record the temperature continuously, the temperature must be logged at least once every working-day. The equipment must have a "memory function" of temperatures (e.g. min/max temperatures are recorded), and the temperature must be logged the next working day after holidays.

No trial IMP should be dispensed to any person not enrolled in the trial.

Unused IMP must be stored separately from used IMP.

The pharmacist must keep an accurate record of all IMP received and the IMP used for each patient in a Drug Accountability Record. Used and partly used IMP will be retained at the investigators site pending review of drug accountability by the monitor.

An IMP may only be destroyed upon instruction from the monitor and will be documented in the Investigator's file.

# 5.1.5 Recall of Investigational Products

In case of recall of investigational medicinal products (decided by the Competent Authorities [CA] or the sponsor), the investigator and the pharmacist will be immediately informed by Innate Pharma.

The investigator and the pharmacist, in collaboration with the study monitor, must urgently:

- o Put the concerned products in quarantine
- o Recall the products dispensed in care units
- Stop the delivery of the concerned investigational medicinal products to the patients

The monitor will organize the return of the recalled product to the sponsor drug supply unit, according to the sponsor procedures.

# 5.1.6 Supply of Other Study Materials

Please refer to the Innate Pharma TMM for further information regarding the auxiliaries for preparation and administration of IPH2201.

# 5.2 IBRUTINIB

Ibrutinib will be supplied commercially.

### 5.3 CONCOMITANT TREATMENTS

### 5.3.1 Permitted

No pre-medication is to be given at 1st administration to avoid masking the potential risk of infusion reactions. However, from the 2nd administration a pre-medication by acetaminophen or anti-histamine drug might be prescribed, at the investigator discretion, if the patient experienced any grade 1 to 3 infusion-related AE at the previous cycle.

Patients should receive all necessary supportive care in the form of treatment or prophylaxis as clinically indicated e.g. transfusion of blood products, antibiotics, anti-histaminics, analgesics.

Corticosteroids by systemic route are prohibited, as mentioned below in section 5.3.2.

Any blood product and/or concomitant medication administered should be recorded in the medical record and eCRF, including dose, start and stop dates.

#### CONFIDENTIAL

Release date: Edition number

GED version

## 5.3.2 Not Permitted

The following concomitant treatments are not permitted until the end of the treatment period (End of Treatment) and must be stopped before the start of treatment accordingly with their pharmacological effects:

- o Any chemotherapy or other systemic anti-tumor therapy (including other monoclonal antibody)
- Any irradiation
- o Corticosteroids IV or *per os* (PO) (except for the treatment of grade ≥ 3 infusion reaction)
- Other Investigational drugs
- o Cytokines and/or growth factors
- Immunosuppressive agents
- o Antivitamin K anticoagulants

Strong CYP3A inhibitors (see appendix V) are contra-indicated if they must be given more than 7 days. If a strong CYP3A inhibitor must be given for 7 days or less consider interrupting ibrutinib until the CYP3A inhibitor is no longer needed.-If a moderate inhibitor (see appendix V) must be given for any time period, the dose of ibrutinib should be reduced to 140 mg. Strong CYP3A inducers (see appendix V) should be avoided with ibrutinib.

# 5.4 ELECTIVE PROCEDURE

Ibrutinib should be discontinued 3 days before and 3 days after a minor procedure (e.g. invasive exploration such as a colonoscopy) and 7 days before and 7 days after a major procedure (e.g. surgery). It is not required to discontinue IPH2201 under those circumstances.

# 5.5 COMPLIANCE

Study treatments must be administered in the investigational center and supervised by a physician or a nurse of the department.

Release date: Edition number

GED version

# 6 STUDY VISITS AND PROCEDURES

# 6.1 INFORMED CONSENT AND SCREENING VISIT

Written informed consent will be obtained from the patient before any study specific procedure is undertaken.

Patients will be informed about the study verbally and by reviewing the patient information sheet and consent form. An additional information sheet and consent form will be given to patients for exploratory examinations (i.e., lymph node punch biopsies and bone marrow examination 4 weeks after the first administration of IPH2201, both of which remain optional). The patient must be given the opportunity to ask questions and time to consider his or her participation. The investigator and the patient will both sign and personally date the consent form as confirmation of consent at the screening visit.

Patients screened for the study must be registered in the IWRS system to receive a screening number.

The start of the screening period should be performed within 3 weeks prior to the planned first study drug administration (Week 0).

The following assessments will be performed at the Screening Visit or during the screening period:

- o Inclusion/Exclusion criteria
- o Demography data: gender, date of birth
- Medical history (including CLL)
- o Concomitant illness, Concomitant medication
- o Tumor assessment
- Safety assessments
  - A full physical examination including height and weight is required at baseline visit
  - Vital signs (heart rate, body temperature, diastolic and systolic blood pressure) (see detailed vital signs in Section 9.2 Safety Assessments)
  - ECOG status
  - 12-Lead ECG
- o Laboratory assessments
  - Hematology: red blood cell(s) (RBC), WBC with differential count, platelets, hemoglobin;
     Mean Corpuscular Volume (MCV), hematocrit
  - Biochemistry: sodium, potassium, chloride, bicarbonate, calcium, magnesium, phosphate, total proteins, and albumin, urea, uric acid, creatinine, calculated creatinine clearance, ALP, total bilirubin, LDH, AST (SGOT), ALT (SGPT), gamma glutamyl transferase (GGT), amylase, lipase, glucose, C-reactive protein (CRP) and fibrinogen
  - Urinalysis: PH, glucose, leucocytes, proteins, blood and hemoglobin
  - Coagulation factors: activated partial thromboplastin time (APTT), prothrombin time (PT)
  - HIV/Hepatitis screen (HBV and HCV)
  - Thyroid gland: TSH, Free T3 and Free T4
- Are required at the end of the screening period and when eligibility criteria have been confirmed:
  - A Bone Marrow aspirate, if not performed within 1 month before the screening visit
  - •
  - Molecular testing and cytogenetics, including detection of genetic abnormalities usually associated to CLL and IgVh mutational status

[figure not shown]

Release date: Edition number

MOD-3783

12 August 2016

GED version

### 6.2 DESCRIPTION OF STUDY CYCLES

The treatment administration visits will be performed every 2 weeks +/- 3 days during 4 cycles (8 weeks), then every 4 weeks +/- 7 days during a maximum of 12 cycles (48 weeks).

Week0 (W0) defines the first dosing visit

H0 is the start time of the 1-hour infusion and also defines the pre-dose assessments.

# 6.2.1 Patients in part 1 - Phase lb

# 6.2.1.1 Cycle 1

Cycle 1 is a 2-week cycle and consists of 3 visits, the dosing visit (W0), a visit 24 hours after dosing (W0D2) and a visit 1 week after dosing (W0D8).

### Week 0 visit (W0)

At week 0 visit, IPH2201 only will be administered.

The following pre-dose assessments must be done prior to IPH2201 administration:

- Inclusion/Exclusion criteria
- Concomitant illness/Concomitant medication
- Safety assessments
  - Vital signs (including weight)
  - Physical examination, focused on symptoms and new findings (from screening visit)
  - o ECOG status
  - o Adverse events
  - o 12-lead ECG
- Pre-dose Safety laboratory (H0)
  - Hematology: red blood cell(s) (RBC), white blood cells (WBC) with differential count, platelets, hemoglobin, Mean Corpuscular Volume (MCV), hematocrit
  - Biochemistry: sodium, potassium, chloride, bicarbonate, calcium, magnesium, phosphate, total proteins, and albumin, urea, uric acid, creatinine, calculated creatinine clearance, ALP, total bilirubin, LDH, AST (SGOT), ALT (SGPT), gamma glutamyl transferase (GGT), amylase, lipase, glucose, C-reactive protein (CRP) and fibrinogen
  - o Pregnancy test
- Pre-dose PK/PD assessments (H0)
  - 0
  - o Pharmacokinetics
  - 0

IPH2201 will be administered as a 1-hour intravenous (IV) infusion, at one of the following dose levels:

Dose level 1: 1 mg/kg Dose level 2: 2 mg/kg Dose level 3: 4 mg/kg Dose level 4: 10 mg/kg

No pre-medication is to be given to avoid masking the potential risk of infusion reactions.

The following post-dose assessments are required at cycle Week 0:

- 12-lead ECG at H0+3 (+ 1 hour)
- Biochemistry at H0+4 (3 hours after end of infusion) sodium, potassium, chloride, bicarbonate, calcium, magnesium, phosphate, total proteins, and albumin, urea, uric acid, creatinine, ALP, total bilirubin, LDH, AST (SGOT), ALT (SGPT), gamma glutamyl transferase (GGT), amylase, lipase, glucose, C-reactive protein (CRP) and fibrinogen
- o Hematology at H0+4 (3 hours after end of infusion): RBC, WBC with differential count, platelets, hemoglobin; MCV, hematocrit
- 0 o PK assessments at H0+1 (at end of IPH2201 infusion) and H0+3 (2 hours after end of IPH2201 infusion)
- 0

